### **6.4.3 Recording of adverse events**

#### **Time period for collection of adverse events**

Adverse events and SAEs will be collected from time of informed consent (ie, in source documents).

For the purpose of this study, non-serious AEs will be recorded in the eCRF only if they occur in the 24 hours immediately following a dose of study drug or increase in intensity in the 24 hours immediately following a dose of study drug, as migraine is an episodic condition and patients will be using study drug only for acute treatment of attacks. Twenty-four hours is more than 5 times the half-life of zolmitriptan and is therefore considered to be in excess of the elimination period for the study drug. Non-serious AEs that lead to patient discontinuation from the study will also be recorded in the eCRF.

Serious adverse events will be recorded in the eCRF if they occur at any point during the study.

#### **Follow-up of unresolved adverse events**

Any AEs that are unresolved at the patient's last AE assessment in the study are followed up by the investigator for as long as medically indicated, but without further recording in the eCRF. AstraZeneca or its representative retains the right to request additional information for any patient with ongoing AEs/SAEs at the end of the study, if judged necessary.

#### **Variables**

The following variables will be collected for each AE:

- AE (verbatim);
- The date when the AE started and stopped (duration of AE);
- Maximum intensity or intensity or changes in intensity;
- Whether the AE is serious or not;
- Investigator causality rating against the study drug (yes or no);
- Action taken with regard to study drug;
- AE caused patient's withdrawal from the study (yes or no);
- Outcome.

In addition, the following variables will be collected for SAEs:

- Date AE met criteria for SAE;
- Date investigator became aware of SAE;
- AE is serious due to;
- Date of hospitalization;
- Date of discharge;
- Probable cause of death;
- Date of death;
- Autopsy performed;
- Causality assessment in relation to study procedure(s);
- Causality assessment in relation to study drug;
- Causality assessment in relation to other medication;
- Description of AE.

Intensity is defined as follows:

- Mild (awareness of sign or symptom, but easily tolerated);
- Moderate (discomfort sufficient to cause interference with normal activities);
- Severe (incapacitating, with inability to perform normal activities).

It is important to distinguish between serious and severe AEs. Severity is a measure of intensity, whereas seriousness is defined by the criteria in Section 6.4.2. An AE of severe intensity need not necessarily be considered serious. For example, nausea that persists for several hours may be considered severe nausea, but not a SAE. On the other hand, a stroke that results in only a limited degree of disability may be considered a mild stroke, but would be a SAE.

If a diagnosis of the patient's condition has been made, then the diagnosis should be recorded as the SAE or the AE. In instances of well-recognized symptoms, they can be recorded as the commonly used diagnosis (eg, fever, runny nose, and cough can be recorded as "flu"). However, if a diagnosis of the patient's condition has not been made, or if the individual symptoms are not well recognized, then the individual symptoms should be recorded separately.

The patient's usual non-headache symptoms of migraine (ie, nausea, vomiting, photophobia, or phonophobia) will not be recorded as AEs. However, migraine symptoms that are atypical or of unusual intensity for the patient must be recorded as AEs.

Where there is a deterioration in the condition for which the study drug is being used, there may be uncertainty as to whether this is normal disease progression (resulting from a lack of efficacy) or an AE. In these circumstances, if it is believed that the study drug did not contribute to the deterioration, then the deterioration should be considered lack of efficacy. However, if it is believed that the study drug may have contributed to the deterioration, then the deterioration should be treated as an AE.

Patients should record all unusual experiences (signs, symptoms, feelings, etc) on the symptom/medication log provided in the patient diary. At the final visit, the investigator should discuss the experience with the patient and, if appropriate, record the experience as an AE on the eCRF provided.

Should an overdose occur, it must be reported in accordance with the procedures described in Section 13.2. All overdoses, with or without associated symptoms, should be reported as AEs.

Suicide and attempted suicide, irrespective of the method, but occurring in connection with the use of the study drug, should be reported as AEs (serious or non-serious). This event should be identified as suicide or attempted suicide, and the method of the suicide or attempt should be provided. If an attempted suicide meets the criteria for an SAE, the event must be reported according to the guidelines in Section 6.4.4. Suicidal thoughts should also be regarded as AEs.

All events of suicidality will be carefully monitored. These include events of suicide attempts, suicidal ideation, completed suicides, and suicidal behavior. The last category includes behavioral AEs or SAEs in which the investigator cannot rule out underlying suicidal thinking, eg, motor vehicle accident or behaving in a dangerous or unsafe way, and other self-injurious behaviors.

Pregnancy in itself is not regarded as an AE unless there is a suspicion that the study drug has interfered with the effectiveness of a contraceptive medication. (To be eligible for this study, females of childbearing potential and at risk of pregnancy must be using a reliable method of contraception; see [inclusion criterion #9](#), Section 4.1). Should a pregnancy occur, it must be reported in accordance with the procedures described in Section 13.3.

In the clinical study report, the terms used by the investigator to record AEs will be mapped to preferred terms using a standard AE dictionary, Medical Dictionary for Regulatory Activities (MedDRA).

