Serotonin syndrome has been reported with combined use of triptans, and selective serotonin re-uptake inhibitors (SSRIs) and serotonin norepinephrine re-uptake inhibitors (SNRIs). Serotonin Syndrome is a potentially life-threatening condition, and may include signs and symptoms such as: mental status changes (eg, agitation, hallucinations, coma), autonomic instability (eg, tachycardia, labile BP, hyperthermia), neuromuscular aberrations (eg, hyperreflexia, incoordination), and/or gastrointestinal symptoms (eg, nausea, vomiting, diarrhea). Careful observation of the patient is advised, if concomitant treatment with zolmitriptan and an SSRI or SNRI is given, particularly during treatment initiation and dosage increases.

All efforts will be taken to minimize risk to patients enrolled in this trial. No patient will be enrolled who has had a previous adverse reaction to zolmitriptan or other triptans. Patients with medical conditions that would put them at increased risk for adverse reactions will also be excluded from this study.

In order to ensure that the population enrolled in the study is representative of the patient population at large, individuals who have medically stable chronic conditions will not be excluded. These patients will not be required to stop their treatment for their chronic conditions (eg, high BP) prior to or during the trial. Of particular concern are those patients who are taking SSRI/SNRIs. Concomitant use of a triptan with an SSRI/SNRI has been associated with the Serotonin Syndrome. To minimize this risk, only patients who have been stabilized on an SSRI or SNRI for at least 2 months will be enrolled and no dosage

adjustments of these agents will be allowed. These patients will also be carefully monitored for any signs and symptoms of the Serotonin Syndrome.

Migraine in adolescents is a debilitating neurological condition. At present, only 2 triptan oral formulations (almotriptan and rizatriptan) are approved for acute treatment of migraine in adolescents. This trial will fully explore the efficacy and safety of zolmitriptan nasal spray as an alternative for the acute treatment of migraine. This single-attack trial is specifically designed to minimize risk to patients while potentially identifying a new treatment option for these patients.

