### **Disease progression, worsening migraine, and migraine-associated symptoms**

Disease progression can be considered as a worsening of a patient’s condition attributable to the disease for which the study drug is being studied. It may be an increase in the severity of the disease under study and/or increases in the symptoms of the disease. The development of worsening migraines should be considered as disease progression and not an AE. Events, which are unequivocally due to disease progression, should not be reported as an AE during the study.

Where there is a deterioration in the condition (ie, worsening migraine) for which the study treatment is being used, there may be uncertainty as to whether this is normal disease progression (resulting from a lack of efficacy) or an AE. Generally speaking, recurrence of

migraines that is otherwise typical for a given patient should not be considered an AE (and is instead considered a lack of efficacy). Additionally, migraine-associated symptoms such as nausea, vomiting, photophobia, or phonophobia should generally not be recorded as AEs if they are typical for a given patient.

In certain circumstances, however, events related to worsened migraine should be considered as AEs:

- Headaches that are clearly atypical or of unusual intensity for a given patient;
- Clinical symptoms that otherwise meet criteria for an SAE (Section 6.4.2).

Migraine symptoms resulting in trial discontinuation should not be counted as AEs unless they also meet at least 1 of the 2 criteria listed above.

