## **6.5 Patient reported outcomes (PRO)**

### **6.5.1 Patient diary (self-assessment of headache pain, symptoms, and treatment response)**

A paper patient diary will be used for date and time stamping of patients' self-assessment of headache pain, symptoms, and treatment response.

Patients will assess migraine pain severity and rate the intensity as severe (3), moderate (2), mild (1), or none (0).

Patients will record the following data relevant to their migraine headaches:

- Headache frequency and type (run-in period only);
- Date and time headache intensity is moderate or severe prior to study treatment (baseline);
- Date and time of treatment with study drug;
- Presence of associated migraine symptoms (photophobia, phonophobia, nausea, vomiting) at baseline;
- Headache intensity prior to treatment with study drug, and at 15 minutes ( $\pm 10$  minutes) and 1 hour ( $\pm 30$  minutes), 2 hours ( $\pm 20$  minutes), 3 hours ( $\pm 30$  minutes), 4 hours ( $\pm 30$  minutes), and 24 hours ( $\pm 8$  hours) after treatment;
- Presence of associated migraine symptoms at 15 minutes ( $\pm 10$  minutes) and 1 hour ( $\pm 30$  minutes), 2 hours ( $\pm 20$  minutes), 3 hours ( $\pm 30$  minutes), 4 hours ( $\pm 30$  minutes), and 24 hours ( $\pm 8$  hours) after treatment;
- Rescue medications taken, time, and date;
- Ability to perform normal activities prior to treatment with study drug, and at 15 minutes ( $\pm 10$  minutes) and 1 hour ( $\pm 30$  minutes), 2 hours ( $\pm 20$  minutes), 3 hours ( $\pm 30$  minutes), 4 hours ( $\pm 30$  minutes), and 24 hours ( $\pm 8$  hours) post treatment;
- Headache recurrence 2 to 24 hours post treatment;
- Bilateral headache (yes/no) prior to treatment with study drug, and at 15 minutes ( $\pm 10$  minutes) and 1 hour ( $\pm 30$  minutes), 2 hours ( $\pm 20$  minutes), 3 hours ( $\pm 30$  minutes), 4 hours ( $\pm 30$  minutes), and 24 hours ( $\pm 8$  hours) post treatment;

- Intensity increased by movement (yes/no) prior to treatment with study drug, and at 15 minutes ( $\pm 10$  minutes) and 1 hour ( $\pm 30$  minutes), 2 hours ( $\pm 20$  minutes), 3 hours ( $\pm 30$  minutes), 4 hours ( $\pm 30$  minutes), and 24 hours ( $\pm 8$  hours) post treatment.

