### **11.1.3 Resolution of associated symptoms of migraine**

Resolution of associated symptoms of migraine is defined for those patients who have associated symptoms at baseline who are then symptom free at the assessment timepoints. Associated symptoms of migraine are photophobia, phonophobia, nausea, or vomiting.

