### **12.2.3 Secondary efficacy variables**

The following secondary efficacy variables will be analyzed for OC and/or LOCF in the FAS:

- Pain-free status at 15 minutes and at 1, 2, 3, 4, and 24 hours post treatment;
- Headache response at 15 minutes and at 1, 2, 3, 4, and 24 hours post treatment;
- Sustained headache response at 2 hours subsequent to a 1-hour headache response;
- Presence of associated symptoms of photophobia, phonophobia, or nausea at 15 minutes and at 1, 2, 3, 4, and 24 hours post treatment;
- Resolution of associated symptoms of photophobia, phonophobia, or nausea at 15 minutes and at 1, 2, 3, 4, and 24 hours post treatment;
- Incidence and time to use of rescue medication up to 24 hours post treatment;
- Ability to perform normal activities at 15 minutes and at 1, 2, 3, 4, and 24 hours post treatment.
- Headache recurrence 2 to 24 hours post treatment;
- Bilateral headache (yes/no) at 15 minutes and at 1, 2, 3, 4, and 24 hours post treatment;
- Intensity increased by movement (yes/no) at 15 minutes and at 1, 2, 3, 4, and 24 hours post treatment.

For the binary secondary efficacy variables, the same logistic regression model as for the analysis of primary efficacy variable will be used. Time to use of rescue medication will be displayed graphically using Kaplan-Meier curves by treatment group. Comparison of treatment doses versus placebo will be based on the Cox proportional hazard model. The secondary endpoints will be analyzed at the 2-sided 5% significance level without any multiplicity correction.

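### Usual-type nausea or vomiting that starts after the dose can be left out of the AE data, the listed endpoints do not isolate it, and vomiting is in the symptom definition but in no endpoint list

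*Protocol*

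**What the plan says.** Two parts of protocol section 6.4.3 keep usual migraine symptoms out of the AE data. Under Variables, the "usual non-headache symptoms of migraine (ie, nausea, vomiting, photophobia, or phonophobia) will not be recorded as AEs". Under Disease progression, worsening migraine, and migraine-associated symptoms, the same symptoms "should generally not be recorded as AEs if they are typical for a given patient".

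The section also sets exceptions. Under Variables, "migraine symptoms that are atypical or of unusual intensity for the patient must be recorded as AEs", and "if it is believed that the study drug may have contributed to the deterioration, then the deterioration should be treated as an AE". The disease-progression text keeps as AEs headaches that are clearly atypical or unusually intense, and symptoms that meet SAE criteria.

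The diary (6.5.1) collects "Presence of associated migraine symptoms (photophobia, phonophobia, nausea, vomiting) at baseline" and, at six times after the dose, the presence of associated migraine symptoms without naming them again. Section 12.2.3 lists as an endpoint "Presence of associated symptoms of photophobia, phonophobia, or nausea at 15 minutes and at 1, 2, 3, 4, and 24 hours post treatment", and resolution of the same three symptoms at the same times. The synopsis, 2.2 and 6.3.1 name the same three. The definition behind resolution is wider: "Associated symptoms of migraine are photophobia, phonophobia, nausea, or vomiting" (11.1.3, and to the same effect in the text of 6.3.1). It applies only to patients with associated symptoms at baseline. Section 12.2.4 lists the incidence, nature and intensity of AEs, but no diary symptoms.

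**The concern.** Safety and tolerability is a stated objective (2.3), and the rationale in 1.3 aims to identify the highest and lowest safe and efficacious dose. Nausea and vomiting can be symptoms of the attack or effects of the drug, so AE counts for them depend on how the two are told apart. The rule tells them apart by the patient's history, not by the pre-dose record of the treated attack. Drug-caused nausea that resembles the patient's ordinary migraine nausea is then filed as migraine.

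That would matter little if an endpoint showed new onset by arm, but none of those listed does. The tolerability comparison between doses could look better than it is. Separately, one secondary endpoint can be computed in two ways from the same protocol.

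**Working it through.** The protocol states no figure on this point, so the check traces each case through the text.

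**Step 1. Where each case is counted.** Take a symptom of the patient's usual type and intensity, with no exception applied. Resolution is read symptom by symptom.

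| Case | AE data | Presence endpoint | Resolution endpoint |
|---|---|---|---|
| Nausea before the dose, persists | no | yes | yes, as not resolved |
| Nausea absent before, starts after | no | yes, pooled with the row above | outside its population |
| Vomiting before the dose, persists | no | not listed | out by the lists, in by the definition |
| Vomiting absent before, starts after | no | not listed | outside its population |

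The last row appears nowhere. If resolution were instead read across all symptoms together, a patient with, say, photophobia before the dose and new vomiting afterwards could count as not symptom-free under the wider definition. The vomiting would still not be identified as new.

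**Step 2. How far the exceptions reach.** Atypical type or unusual intensity does not cover a symptom that looks ordinary. The drug-contribution clause needs a belief that the drug played a part, and a familiar symptom gives little ground for that. The SAE clause covers only serious events. The patient's log asks for unusual experiences, which an ordinary symptom is not. The exceptions narrow the gap without closing it.

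**Step 3. AE undercount, illustration.** Assume a true drug-caused excess of 5 points, independent of whether the symptom is usual, and no exception applied. With a share u of patients who usually have the symptom, the excess seen in the AE table is 5 × (1 − u):

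- u = 20%: 5 × 0.8 = 4.0 points
- u = 50%: 5 × 0.5 = 2.5 points
- u = 80%: 5 × 0.2 = 1.0 point

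**Step 4. Presence of nausea, a separate illustration.** Presence = b × persistence + (1 − b) × onset, where b is the share with nausea before the dose. Assume persistence of 50% on placebo and 40% on drug, and onset among symptom-free patients of 5% and 15%.

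| b | Placebo | Drug | Difference in presence | Difference in new onset, all patients |
|---|---|---|---|---|
| 40% | 0.20 + 0.03 = 23% | 0.16 + 0.09 = 25% | +2 | 0.6 × 10 = +6 |
| 60% | 0.30 + 0.02 = 32% | 0.24 + 0.06 = 30% | −2 | 0.4 × 10 = +4 |
| 80% | 0.40 + 0.01 = 41% | 0.32 + 0.03 = 35% | −6 | 0.2 × 10 = +2 |

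Onset is tripled in every row, yet presence favours the drug in two of the three. The sign changes at b = 50%, which follows from the assumed 10-point effects in opposite directions. Steps 3 and 4 assume different harms and should not be combined.

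**The case against.** The strongest reply has four parts.

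- **Exclusion is not absolute.** A reader might infer that usual nausea and vomiting are barred from the AE data outright. They are not: the exceptions are explicit, the second wording is softened, and investigators review the patient's log. This stands, and it limits the point to symptoms of ordinary type and intensity.
- **Nausea is still counted.** A reader might infer that drug-caused nausea is reported as absent, or that presence is the only symptom endpoint. Nausea present at an assessment time enters the presence comparison by arm, and resolution is an endpoint too. This stands. What is lost is the separation of new onset from persistence.
- **A new-onset table is analysis-plan detail.** The data are collected, nothing in the protocol forbids the table, and the SAP is not shown. This stands in part: the absence of the table is not an error in itself. But the AE rule and the two versions of the symptom list are protocol text. An analysis plan cannot restore AEs that were never recorded, and it would have to depart from one of the two versions.
- **The sizes are assumed.** This stands. Nothing in the documents supports particular values for usual symptoms, persistence or onset.

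A reader might also infer that the AE rule contradicts the promise in 1.4 to monitor SSRI/SNRI users for serotonin syndrome, since nausea and vomiting are among its listed signs. The documents do not support that. Section 1.4 describes a syndrome with several possible components and commits to clinical observation, and 6.4.3 has a diagnosis recorded as the AE.

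**Conclusion.** The point holds in a limited form. As written, the protocol can understate treatment-emergent nausea and vomiting in the AE tables, and post-dose vomiting of the usual kind may appear in no listed endpoint. The inconsistency on vomiting stands whatever the SAP contains, but it does not mean that vomiting is wholly ignored: the definitions in 6.3.1 and 11.1.3 include it, and the lists do not. The direction of the AE effect follows from the rule, provided that the drug causes some such symptoms and the exceptions do not catch them all. Its size cannot be derived from the documents. The primary analysis is unaffected. The change is worth making because it costs little, but the trial's main conclusion does not depend on it.

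**What to change.** 1. In 12.2.4, add a diary-based safety summary on the safety analysis set. For nausea and for vomiting separately, give the number and percentage per arm of patients without the symptom at the pre-dose record who report it at any post-dose record up to 24 hours. Show the number at risk as well.
2. Reconcile the endpoint lists in the synopsis, 2.2, 6.3.1 and 12.2.3 with the definition in 6.3.1 and 11.1.3, so that vomiting is either in all of them or in none. Either choice settles the resolution endpoint. The safety table is needed in both cases.
3. Confirm in 6.5.1 that the post-dose diary item covers the same four symptoms as the baseline item. Only the baseline item names vomiting, and the table depends on it being asked afterwards.

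The AE recording rule stays as it is. The cost is one table and some wording, with no added visits and, if item 3 is confirmed, no added data collection. The small downside is that natural evolution of an attack counts as new onset, so the table must be read against the placebo arm.

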### **Causality collection**

The investigator will assess causal relationship between the study drug and each AE (ie, their relationship to study drug), and answer "yes" or "no" to the question, "*Do you consider that there is a reasonable possibility that the event may have been caused by the study drug?*"

For SAEs, causal relationship will also be assessed for other medication and study procedures. Note that for SAEs that could be associated with any study procedure, the causal relationship is implied as “yes.”

A guide to the interpretation of the causality question is found in [Appendix B](#) to the CSP.

### **Adverse events based on signs and symptoms**

All AEs spontaneously reported by the patient or reported in response to the open question from the study personnel, “*Have you/the child had any health problems since the previous visit/you were last asked?*” or revealed by observation will be collected and recorded in the eCRF. When collecting AEs, the recording of diagnoses is preferred (when possible) to recording a list of signs and symptoms. However, if a diagnosis is known and there are other signs or symptoms that are not generally part of the diagnosis, the diagnosis and each sign or symptom will be recorded separately.

